## 7.3. Objective 1: 5-Year Superiority

Five-year superiority will be evaluated by testing the hypothesis that the coflex device in conjunction with surgical decompression is superior to decompression alone at five years. This objective will be met by testing the following superiority hypotheses:

**Ho:  $CCS_{coflex+decomp.} - CCS_{decomp} \leq 0$  (not superior)**  
**Ha:  $CCS_{coflex+decomp.} - CCS_{decomp} > 0$  (superior)**

An informative prior based on final 5-year IDE study results for the coflex group will be used as described below. A non-informative prior will be used for the decompression alone group. The Bayesian posterior probability that  $(CCS_{coflex+decomp.} - CCS_{decomp.}) > 0$  will be determined.

**If the posterior probability is  $\geq 0.95$  then superiority will be concluded.**

#### 7.4. Objective 2: 2-Year Non-Inferiority

Two-year non-inferiority will be evaluated by comparing clinical status of patients implanted with the coflex® device in conjunction with surgical decompression relative to surgical decompression alone at two years post operatively by confirming clinical non-inferiority in terms of Month 24 composite clinical success (CCS) defined similarly to the IDE study endpoint. To meet this objective, the following hypotheses will be tested:

**Ho:  $CCS_{coflex+decomp.} - CCS_{decomp.} \leq -0.10$  (inferior)**

**Ha:  $CCS_{coflex+decomp.} - CCS_{decomp.} > -0.10$  (not inferior)**

**Non-inferiority will be concluded if the posterior probability is at least equal to 0.95.**

#### 7.5. Objective 3: 2-Year Superiority

If 2-year non-inferiority is demonstrated, the following superiority hypotheses will be tested.

**Ha:  $(CCS_{coflex+decomp.} - CCS_{decomp.}) \leq 0$ .**

**Ha:  $(CCS_{coflex+decomp.} - CCS_{decomp.}) > 0$ .**

This will be done by determining the Bayesian posterior probability that  $(CCS_{coflex+decomp.} - CCS_{decomp.}) > 0$ . The same informative prior for the coflex® group only will be used. If the posterior probability is  $\geq 0.95$  then superiority will be concluded.

#### 7.6. Objective 4: Real Conditions of Use

Coflex device performance will be evaluated in a “real conditions of use” study by testing the hypothesis that device performance is not clinically inferior in the PAS population relative to device performance defined by IDE study results. Patients will be enrolled from sites that were not involved in the IDE study. The same Month 24 composite clinical success (CCS) endpoint used in the IDE trial will be used in analyses to facilitate this comparison.

**Ho:  $CCS_{PAS} \leq 0.662 - 0.10 = -0.562$  (inferior)**

**Ha:  $CCS_{PAS} > 0.662 - 0.10 = -0.562$  (not inferior).**

**Non-inferiority will be concluded if the posterior probability is at least equal to 0.95.**

If the inferiority hypothesis is rejected, then the numbers of coflex® successes and failures observed in the PAS will be used to update the Bayesian posterior probabilities of non-inferiority and superiority relative to fusion that were first established in the IDE study and reported in the coflex® SSED. This will facilitate a formal accumulation and summary of what has been learned about the relative effectiveness of coflex® compared to fusion based on pooling relevant information from the IDE trial and this PAS. As reported in the coflex® SSED, the Bayesian posterior probability that coflex® is not clinically inferior to fusion ( $\delta=-0.10$ ) is 0.999362. Similarly, the Bayesian posterior probability that coflex® is superior to fusion in terms of Month 24 CCS was reported to be equal to 0.927550.

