	
<math>CCS_{decomp}) > 0</math>. Superiority will be concluded if the posterior probability is at least equal to 0.95.
 
Objective 4: (real conditions of use): The following hypotheses will be tested in order to evaluate whether or not coflex® device performance is clinically inferior in the PAS population compared to the IDE population using a non-inferiority <math>\delta=-0.1175</math>. The following hypotheses will be tested.
 
Ho: <math>CCS_{PAS} \leq CCS_{IDE} - 0.1175</math>
 
Ha: <math>CCS_{PAS} > CCS_{IDE} - 0.1175</math>.
 
Non-inferiority of coflex performance in the PAS population will be concluded if the posterior probability that (<math>CCS_{PAS} > CCS_{IDE} - 0.1175</math>) is at least 0.95.
 
Sample Size Analysis Details concerning the Bayesian simulations for this study were previously reviewed and are included in Bayesian Simulations Memo, Version 4.1, May 5, 2015.
 
Objective 1: (5-year superiority) These Simulations were used to evaluate the power and type 1 error for determining superiority of coflex® in conjunction with surgical decompression relative to surgical decompression alone at Month 60. For the purpose of these simulations it was assumed that the Month 60 success rate would be 0.57 for coflex®. A posterior probability threshold of at least 0.95 was selected. Power was found to be equal to 83% if the true superiority margin is 12.5%. If the true superiority margin is only 10%, then power to conclude superiority is reduced to 65%. Type 1 error was determined through simulation by assuming that the probabilities of Month 60 success were equal to 0.57 for both device groups. The estimated type 1 error rate is equal to 0.037(SD=0.0011) based on an average of 10 identical simulations with varying randomization seeds.
 
Objective 2: (2-year non-inferiority) Bayesian simulations were performed to evaluate the operating characteristics for testing the Objective 1 hypothesis non-inferiority hypothesis. In the pivotal IDE study, 135 of 204 patients (66.2%) achieved Month 24 CCS. These results were used to define the prior distribution for coflex in conjunction with surgical decompression as beta (135.5, 69.5) since the distribution prior to the IDE trial was specified as beta (0.5, 0.5). This Jeffries non-informative prior was assumed for patients undergoing decompression alone. A non-inferiority margin of -0.10 is specified. Non-inferiority will be concluded if the Bayesian posterior probability that (<math>CCS_{coflex+decomp} - CCS_{decomp}) > -0.10</math> is at least equal to 0.95. When evaluating

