**Objective 4: (real conditions use)**

A design was identified that uses a non-inferiority margin of -0.1175 and a 0.95 posterior probability threshold. This design has an estimated type 1 error that of 0.045 and power of about 80%. Other assumptions include expected success rates 0.662 in both groups when determining power.

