### 7.7.1. Objective 1: 5-Year Superiority

These simulations were used to evaluate the power and type 1 error for determining superiority of coflex in conjunction with surgical decompression relative to surgical decompression alone at Month 60. For the purpose of these simulations it was assumed that the Month 60 success rate would be 0.57 for coflex®. The prior distribution derived in the Memo is beta(82.1,62.1) reflecting a 20% discount off of a total prior sample size of N=179. Power was found to be equal to 83% if the true superiority margin is 12.5%. If the true superiority margin is only 10%, then power to conclude superiority is reduced to 65%. Type 1 error was determined through simulation by assuming that the probabilities of Month 60 success were equal to 0.57 for both treatment groups. The estimated type 1 error rate is equal to 0.037(SD=0.0011) based on an average of 10 identical simulations with varying randomization seeds.

It may be now be noted that subsequent to the Bayesian design memo submission, the final results from the PMA study were submitted to FDA in the Final Report (P110008/R014). The Month 60 PAS CCS was achieved in 55.9% (104/186) patients which is very close to the projected success rate of 57%. The total sample size of 186 is slightly larger than the assumed 179 which implies a discount of the prior of 23% rather than 20%. Sensitivity analyses (see Table 4 from Bayesian Memo) were provided that demonstrate that type 1 error is 0.040, still below 0.05, if the true success rate is 56% rather than 57%.

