#### **7.7.4. Objective 4: Real Conditions of Use**

Non-informative priors were assumed for the both comparisons groups, since IDE results cannot be used as the basis of an informative prior if the comparison is to be made to that same IDE trial. However, the Bayesian simulation R function was modified to reflect that it is known that exactly 135 successes were observed among 204 evaluable patients in the coflex IDE analysis set (see Simulation Report, Section 8.3). Otherwise, all other features of the Bayesian simulation were kept the same.

A design was identified that uses a non-inferiority margin of -0.1175 and a 0.95 posterior probability threshold. This design has an estimated type 1 error of 0.045 and power of about 80%. Other assumptions include expected success rates 0.662 in both groups when determining power and assuming that the Month 24 success rate in the PAS population is 0.10 smaller than in the IDE study population for evaluating type 1 error.

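### Objective 4 is given two different margins (0.10 and 0.1175), and the Objective 1 imputation steps return a non-inferiority probability with an undefined delta

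*Combined protocol and SAP*

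**What the plan says.** **Objective 4.** Section 7.6 compares the post-approval success rate with a constant, "0.662 - 0.10 = -0.562", in both the null and the alternative. The synopsis hypotheses use "CCS_{IDE} - 0.1175" instead. Section 7.7.4 agrees with the synopsis: "A design was identified that uses a non-inferiority margin of -0.1175 and a 0.95 posterior probability threshold". It adds that both groups have non-informative priors and that "it is known that exactly 135 successes were observed among 204 evaluable patients in the coflex IDE analysis set". The synopsis sample-size text reports: "This design has an estimated type 1 error that of 0.045 and power of about 80" per cent. Section 7.7.4 gives the same figures and says where the error was evaluated: the assumed "success rate in the PAS population is 0.10 smaller than in the IDE study population for evaluating type 1 error".

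**Objective 1.** Section 7.3 asks for the posterior probability that the difference (coflex minus decompression) exceeds 0. If it reaches 0.95, "then superiority will be concluded". Section 7.7.1 gives the Month 60 coflex prior: "The prior distribution derived in the Memo is beta(82.1,62.1"). Section 7.11.1 says its imputation method serves the Month 60 superiority hypothesis and is the primary analysis, with a similar method for the other objectives. Step 4 carries the same 82.1 and 62.1. Step 5 then counts draws in which the difference is at least minus delta and calls the result a probability of non-inferiority. Step 6 averages this over 20 imputations. The section gives delta no value.

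**The concern.** A confirmatory objective needs one decision rule, and its error rate should be evaluated at the boundary of that rule's null. Objective 4 has two margins. Its benchmark is a fixed 0.662 in section 7.6 but carries uncertainty in section 7.7.4. The synopsis writes the IDE rate as a quantity in the hypothesis without saying how it is handled. The 0.045 is attached to the 0.1175 design but was computed at the boundary of the 0.10 design. Passing Objective 4 also decides whether the posterior probabilities against fusion are updated.

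For Objective 1, the algorithm that produces the primary result does not return the quantity that section 7.3 compares with 0.95. Delta cannot safely be borrowed from elsewhere: it appears as 0.10 in section 2, as -0.10 in section 7.6 and as -0.1175 in the synopsis. A negative delta put into 'at least minus delta' would reverse the direction of the margin.

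**Working it through.** **Inputs.** IDE result 135/204 = 0.662 (7.7.2, 7.7.4); 150 coflex patients (4.2); posterior threshold 0.95; true rate 0.662 for power. Section 7.7.4 says only that the priors are non-informative. I assume Beta(0.5, 0.5); Beta(1, 1) gives the same pass marks at N=150.

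**Objective 4 boundaries.** 0.662 - 0.10 = 0.562. 0.662 - 0.1175 = 0.5445. The printed -0.562 is a threshold that every success rate exceeds.

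**Objective 4 rules.** With x successes in 150, the post-approval posterior is Beta(0.5 + x, 150.5 - x). The IDE posterior is Beta(0.5 + 135, 0.5 + 69) = Beta(135.5, 69.5). The pass mark is the smallest x with posterior probability at least 0.95. Rejection probability and power are exact binomial upper tails at that x.

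| Rule | Pass mark | Power at 0.662 | Rejection at 0.562 | Rejection at 0.5445 |
|---|---|---|---|---|
| 7.6: fixed 0.562 | 95/150 | 79.7% | 0.046 | 0.017 |
| 7.7.4: margin 0.1175, IDE posterior | 95/150 | 79.7% | 0.046 | 0.017 |
| Hybrid: margin 0.10, IDE posterior | 97/150 | 68.8% | 0.022 | 0.007 |
| Hybrid: fixed 0.5445 | 92/150 | 91.0% | 0.118 | 0.053 |

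At x = 94 both written rules give a posterior probability of 0.945. At x = 95 they give 0.962 (7.6) and 0.959 (7.7.4).

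The first two rows reproduce the plan's 0.045 and 80%, but the 0.045 is the rejection probability at 0.562. At the 0.1175 rule's own boundary it is 0.017 with the IDE result held at 135/204. If the IDE result is treated as random, Binomial(204, 0.662), full enumeration gives 0.051 at 0.5445 and power 75%.

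Over N = 120 to 186 the two written rules have the same pass mark at 62 of 67 sample sizes. They differ by one patient at N = 163, 168, 173, 178 and 183. Under Beta(1, 1) priors they differ by one patient at six sizes: 121, 126, 131, 136, 178 and 183.

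**Objective 1.** Posteriors as in step 4: Beta(82.1 + S, 62.1 + F) for coflex and Beta(1 + S, 1 + F) for control. I enumerated every outcome with 150 per arm and passed those with posterior probability at least 0.95.

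- Cut-off 0, both true rates 0.57: type I error 0.036 (plan 0.037).
- Cut-off 0, 0.57 v 0.445: power 82.3% (plan 83%).
- Cut-off 0, 0.57 v 0.47: power 64.7% (plan 65%).

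The plan's own figures therefore belong to the superiority rule in section 7.3. If step 5 were run with a positive delta, the chance of passing at equal rates of 0.57 would be 0.09 for delta 0.02, 0.25 for 0.05 and 0.67 for 0.10. These deltas are assumptions; only 0.10 appears in the plan, as Objective 2's margin.

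**The case against.** On Objective 4, the two rules that are written out give the same decision at N=150, and nothing is inflated: with the IDE data held fixed, 0.045 overstates the error at the 0.1175 boundary. The 0.1175 may be a tuned setting chosen to hold rejection below 0.05 at a 0.10 deficit; section 7.7.4 is open about the evaluation point. The synopsis notation and its mention of two groups also lean towards the two-group form. The extreme pass marks come from combinations that no section writes in full. The simulation memo and report, which are not in the document, may settle the matter.

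On Objective 1, section 7.3 is clear, section 7.11.1 itself names a superiority hypothesis, and steps 5 and 6 read like text carried over from a non-inferiority template. Delta = 0 is the only value consistent with section 7.3.

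Much of this stands as a limit on the consequence: the Objective 4 rules agree at the planned size, and the intended Objective 1 test is not in doubt. It does not remove the contradictions. The tuning explanation is not stated, and the synopsis prints 0.1175 inside the hypotheses. Agreement at N=150 depends on pairing each margin with its own benchmark, which the synopsis does not spell out. No text ranks section 7.3 above the algorithm named as the primary analysis.

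One further point stands: step 4's priors belong to Month 60. Section 7.7.2 gives Beta(135.5, 69.5) and Beta(0.5, 0.5) for the two-year comparison, so changing the cut-off alone does not make the algorithm fit Objectives 2 and 3.

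**Conclusion.** The concern holds and should be fixed. Objective 4 has two stated margins, a sign error in its printed threshold, and a type I error quoted at the boundary of one rule while attached to the other. The effect at N=150 is nil if either written rule is applied whole, and one patient at a few other sample sizes. If the parts are mixed, the pass mark ranges from 92 to 97 of 150 and power from 91% to 69%. There is no hidden inflation in either written rule at N=150: with IDE held at 135/204, rejection is 0.046 at 0.562 and 0.017 at 0.5445.

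For Objective 1, steps 5 and 6 cannot be run as written and disagree with section 7.3. The stated operating characteristics are those of a cut-off of 0.

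These figures rest on complete data without propensity-score weighting, exact enumeration in place of simulation, and the assumed non-informative priors for Objective 4. The Objective 1 pass rates for non-zero delta show sensitivity to a value the plan does not give; they do not describe the plan's own rule.

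**What to change.** State one Objective 4 rule, in the same words, in the synopsis hypotheses, the synopsis sample-size text, section 7.6 and section 7.7.4. Either option serves:

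- **Option A.** Posterior probability that the post-approval rate exceeds 0.562 is at least 0.95, with the IDE rate fixed at 0.662. Type I error 0.046 at 0.562; power 80% at N=150.
- **Option B.** Posterior probability that the post-approval rate exceeds the IDE rate minus 0.1175 is at least 0.95, with IDE posterior Beta(135.5, 69.5). Type I error at 0.5445 is 0.017 given 135/204, and 0.051 if the IDE result is treated as random. Power is 80% and 75% respectively at N=150.

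Correct -0.562 to 0.562, or delete it. If 0.1175 was tuned to control error at a 0.10 deficit, say so.

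In section 7.11.1, replace the criterion in steps 5 and 6 with the proportion of draws in which the difference exceeds 0 for Objectives 1 and 3, exceeds -0.10 for Objective 2, and meets the chosen rule for Objective 4. Name the result superiority or non-inferiority accordingly, and list the step 4 priors for each objective alongside the cut-offs.

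Make the change before outcomes are unblinded. It costs wording only, with no change to sample size or data collection. Both Objective 4 options keep 95/150 at N=150; because they can differ by one patient at other sizes, the choice should not wait until the analysed number is known.

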	
before the exact surgical two-year anniversary. In the decompression alone group, since there is no device, this endpoint will be identified as any serious AE that is classified as definitely related to surgery.
 
Note: The IDE study defined this CCS component as severe and definitely-related. This has been changed to serious and definite for consistency with other spine studies for Objectives 2 and 3 only.
 
Objective 4: Month 24 CCS
 
The identical Month 24 CCS endpoint defined for the IDE study will be used to compare PAS results to IDE study results. These results will be used to update the Bayesian posterior probabilities of non-inferiority and superiority relative to fusion that are summarized in the coflex® SSED.
 
Secondary Criteria:
 
 
• ODI change compared to baseline at 24 and 60 months as a continuous variables and in terms of achieving at least a 15 point improvement.
 
• Change in Visual Analog Scale (VAS) for low back pain (on the 100 mm scale) after 24 and 60 months compared to baseline as a continuous variables and in terms of achieving a 20 point improvement.
 
• Change in leg pain using a Visual Analog Scale (VAS) 100 mm scale after 24 and 60 months compared to baseline as a continuous variable and in terms of achieving a 20 point improvement.
 
• Change in worst leg pain using Visual Analog Scale (VAS) 100 mm scale after 24 and 60 months compared to baseline as a continuous variable and in terms of achieving a 20 point improvement
 
• Change of Zurich Claudication Questionnaire (ZCQ) after 24 and 60 months compared to baseline:               
 
1. Symptom severity (range 1-5)
 
2. Physical function (range 1-4)
 
3. Patient satisfaction (range 1-4, no baseline)
 
4. ZCQ Overall Success (<math>\geq 2</math> of 3 of the following)                   
 
1) Improvement in symptom severity <math>\geq 0.5</math>
 
2) Improvement in physical function <math>\geq 0.5</math>
 
3) Satisfied or somewhat satisfied as defined by a score of <math>\leq 2.5</math> points on the patient satisfaction domain.
 
 
 
5. ZCQ Overall Success components
 
 
 
• Maintenance or improvement in EQ-5D compared to baseline
 

--	---

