Most importantly, 66.2% of coflex® and 57.7% of fusions achieved the FDA Month 24 composite clinical success (CCS-IDE) criterion. Based on these pivotal IDE trial results, the Bayesian posterior probability that coflex® is clinically non-inferior to fusion ( $\delta=0.10$ ) at Month 24 was determined to be  $>0.999$  using non-informative Jeffries prior distributions for both treatment groups. Similarly, the Bayesian posterior probability of coflex® superiority relative to fusion at Month 24 was 0.928. The overall adverse event rate was similar between the groups. At 2 years fusions exhibited significantly increased angulation ( $p=0.002$ ) and a trend towards increased translation ( $p=0.083$ ) at the superior adjacent level, while coflex® maintained normal operative and adjacent level motion. With this data, the FDA determined coflex® interlaminar stabilization to be a safe and efficacious alternative, with certain advantages over lumbar spinal fusion in the treatment of spinal stenosis and low-grade spondylolisthesis.

This randomized multicenter study generated the following peer-reviewed publications:

- Decompression and coflex interlaminar stabilization compared to decompression and instrumented spinal fusion for spinal stenosis and low-grade degenerative spondylolisthesis: Two-year results from the prospective, randomized, multicenter food and drug administration investigational device exemption trial. Davis RJ, Errico TJ, Bae H, Auerbach JD. Spine (Phila Pa 1976) 38(18): 1529-1539, 2013.

 Samani J, Study of a semi rigid interspinous "U" fixation system, 106 patients over six years, Spinal surgery, Child Orthopaedics, 1707, 2000

 Kaech DL et al., The interspinous "U": new restabilization device for the lumbar spine, Spinal Restabilization Procedures, Chapter 30, 355 – 362, 2002, Elsevier Science

- Can low-grade spondylolisthesis be effectively treated by either coflex interlaminar stabilization or laminectomy and posterior spinal fusion? Two-year clinical and radiographic results from the randomized, prospective, multicenter US investigational device exemption trial. Davis RJ, Auerbach JD, Bae H, Errico TJ. J Neurosurgery Spine 19(2): 174-184, 2013.
- Mitigating adverse event reporting bias in spine surgery. Auerbach JD, McGowan KB, Halevi M, Gerling MC, Sharan AD, Whang PG, Maislin G. The Journal of Bone and Joint Surgery 95(16): 1450-1456, 2013.

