### **3.2. Primary Endpoints**

The identical Month 24 CCS endpoint as was used in the IDE will be used to compare PAS results to IDE study results, and to update the Bayesian posterior probabilities of non-inferiority and superiority relative to fusion. This CCS definition requires no Treatment Failure (i.e., no reoperation, revision, replacement, or supplemental fixation at the index level(s) and no epidural injection at any lumbar level); an ODI improvement  $\geq 15$ ; as well as no new or worsening, persistent neurological deficit; and no major device-related adverse event defined as severe and definitely-related

The CCS endpoints using in Objective 2 and 3 replace severe device-related AEs with serious device-related AEs for greater consistency with other spine studies. The relationship will be evaluated relative to the device and the surgical procedure since controls receive no device. For comparison to decompression alone, any surgical intervention at the index site will imply clinical failure.

Month 60 success for this comparison will require the following items:

- At least a 15 point improvement relative to pretreatment baseline in the Oswestry Disability Index (ODI, range 0-100).
- No reoperations, revisions, removals, or supplemental fixation at the index level(s);
- No  $\geq 2$  injections or series of injections for any lumbar level\*\*, or nerve block procedures performed to treat spinal stenosis at any lumbar level(s); or a single injection within 12 months of the 5 year endpoint.

\*\*A series of injections is considered 2-3 injections performed between 24-hour and one week intervals designed to treat a single pain event. Secondary injections performed due to patient demand or recurrence of symptoms following the initial injection are considered separate injections and would constitute a study failure.

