### 7.7.2. Objective 2: 2-Year Non-Inferiority

Bayesian simulations were performed to evaluate the operating characteristics for testing the Objective 2 non-inferiority hypothesis. In the pivotal IDE study, 135 of 204 patients (66.2%) achieved Month 24 CCS. These results were used to define the prior distribution for coflex® in conjunction with surgical decompression as beta (135.5, 69.5) since the distribution prior to the IDE trial was specified as beta (0.5, 0.5). This Jeffries non-informative prior was assumed for patients undergoing decompression alone. A non-inferiority margin of -0.10 is specified. Non-inferiority will be concluded if the Bayesian posterior probability that ( $CCS_{coflex+decomp.} - CCS_{decomp.} > -0.10$ ) is at least equal to 0.95. When evaluating statistical power, it was assumed that the true success rate 0.662 for patients treated with coflex®. However, preliminary results from the German decompression study suggest some an advantage of coflex® over decompression alone. Therefore, when evaluating power, Month 24 CCS for decompression alone was assumed to be at least 2% lower, or 0.642. In contrast, Type 1 error was evaluated by assuming that the coflex® success rate 0.662 but that the success rate for decompression was 0.10 larger. With N=150 patients per group, power was shown to be 89%; and type 1 error was shown to be 0.042 and 0.052 'prior to the prior' and with the prior engaged, respectively.

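### The coflex-versus-fusion probabilities are updated with PAS data only if Objective 4 succeeds, which limits how far the superiority figure can fall; the synopsis, 3.2 and 5.1 omit this condition

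*Combined protocol and SAP*

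**What the plan says.** Section 7.6 first tests whether coflex performance in the PAS is inferior to that in the IDE study. It then says: "If the inferiority hypothesis is rejected, then the numbers of coflex" successes and failures from the PAS will update the coflex-versus-fusion probabilities. It describes this update as a formal accumulation of evidence from the two studies. Section 3.1, Objective 4, sets the same condition.

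Three other places state the update with no condition:

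- Synopsis, Objective 4: "These results will be used to update the Bayesian posterior probabilities of non-inferiority and superiority relative to fusion".
- Section 3.2, which uses the IDE endpoint "to update the Bayesian posterior probabilities of non-inferiority and superiority relative to fusion".
- Section 5.1, last paragraph, in near-identical words.

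The starting values are those reported at the end of the IDE trial. Section 7.6 gives 0.999362 for the probability that coflex "is not clinically inferior to fusion" (margin 0.10), and says the probability that coflex "is superior to fusion in terms of Month 24 CCS was reported to be equal to 0.927550". No section says which fusion probabilities are reported if Objective 4 fails.

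**The concern.** A pooled summary should take in the new data whichever way they point. Here the decision to pool depends on the coflex success count that would be pooled. A low count is left out; a high count goes in however far it exceeds the IDE rate. A check that the two populations agree would also stop pooling when the PAS rate is much higher, so the condition is not such a check.

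Two things are at stake. The accumulated probability is biased upward as a summary of both studies. And if Objective 4 fails, the document supports two different outputs (update or no update), so the choice would be made with the results known.

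**Working it through.** **Inputs**

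- Coflex, IDE, Month 24: "135 of 204 patients (66.2"%), section 7.7.2; failures 204 − 135 = 69.
- Fusion, IDE, Month 24: "57.7% of fusions achieved the FDA Month 24 composite clinical success", section 2. The evaluable number is not given; 107 were enrolled.
- Priors for the fusion comparison: "using non-informative Jeffries prior distributions for both treatment groups", section 2, so beta(0.5, 0.5) in each group.
- Objective 4: margin 0.1175 and threshold 0.95 (synopsis, 7.7.4); margin 0.10 in the 7.6 hypotheses.
- PAS coflex patients: 150 planned for analysis, 186 enrolled (section 4.2).

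**Step 1. Reproduce the published figures.** For independent beta posteriors,

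P(p_C − p_F > d) = ∫ f_F(x) · [1 − F_C(x + d)] dx.

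With coflex beta(135.5, 69.5) and fusion beta(60.5, 44.5), that is 60/104 = 57.7%, the result is 0.927550 at d = 0 and 0.999362 at d = −0.10. Both match section 7.6. The other count tried that rounds to 57.7%, 56/97, gives 0.921972 and 0.999175. So 60/104 is inferred, but it fits.

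**Step 2. Find the passing count for Objective 4.** With s successes in 150, PAS is beta(s + 0.5, 150 − s + 0.5) and IDE is beta(135.5, 69.5). The posterior P(p_PAS > p_IDE − 0.1175) is 0.9455 at s = 94 and 0.9586 at s = 95. Objective 4 therefore passes at 95/150 (63.3%) or more. As a check, the exact binomial chance of at least 95 successes is 0.797 at a true rate of 0.662 (plan: about 80%) and 0.0458 at 0.562 (plan: 0.045). This rule matches the stated design.

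**Step 3. Update the fusion comparison.** Coflex becomes beta(135.5 + s, 69.5 + 150 − s); fusion is unchanged.

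| PAS successes of 150 | Objective 4 | Updated superiority probability |
|---|---|---|
| 78 | fails | 0.676 |
| 84 | fails | 0.779 |
| 90 | fails | 0.861 |
| 93 | fails | 0.893 |
| 94 | fails | 0.903 |
| 95 | passes | 0.912 |
| 96 | passes | 0.920 |
| 97 | passes | 0.9275 (just under 0.92755) |
| 99 | passes | 0.941 |
| 105 | passes | 0.971 |

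The figure falls when s is 97 or fewer, and is updated when s is 95 or more. Three counts therefore pass and lower it; the chance of one of these is 17% at a true PAS rate of 0.662, 18% at 0.62 and 12% at 0.60. All larger falls are withheld.

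**Step 4. Average effect.** Weight each count by its binomial probability and let 0.92755 stand when Objective 4 fails.

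| True PAS rate | Expected figure with the condition | Without it |
|---|---|---|
| 0.662 | 0.946 | 0.935 |
| 0.62 | 0.931 | 0.882 |
| 0.60 | 0.929 | 0.850 |
| 0.562 | 0.9275 | 0.773 |

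With the condition, the expected figure barely moves as the device rate drops by 10 points.

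**Step 5. Non-inferiority figure.** At 94/150 the update gives 0.999365, against 0.999362 published; at 95/150 it gives 0.99948. So at n = 150 under this rule no passing count lowers it. The withheld change is small: 0.996 at 84/150.

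**Step 6. Other readings of the rule.** The lowest superiority probability that the condition lets through is:

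| Rule | n = 150 | n = 186 |
|---|---|---|
| Both rates as betas, margin 0.1175 | 0.912 (95 successes) | 0.894 (116) |
| Both rates as betas, margin 0.10 | 0.9275 (97) | 0.926 (120) |
| IDE rate fixed at 0.662, margin 0.10 | 0.912 (95) | 0.894 (116) |
| IDE rate fixed at 0.662, margin 0.1175 | 0.883 (92) | 0.865 (113) |

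**The case against.** A reader might infer that unfavourable PAS data can never lower the published superiority figure. The documents do not support that. Objective 4 compares the PAS with the IDE rate minus a margin, not with the rate at which the fusion probability breaks even, so 95 to 97 of 150 pass and lower it. Single examples also depend on the rule: 93/150 fails with both rates as betas (0.929) but passes if 0.662 is taken as fixed with margin 0.1175 (0.969). The finding on the non-inferiority figure is likewise specific to n = 150 and the Step 2 rule.

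The condition has a rationale. The PAS adds only coflex patients, from sites outside the IDE study, and the fusion data remain those of the randomised IDE controls. If the PAS population does worse, pooling its coflex patients with IDE fusion patients mixes populations. This stands, and it is why the updated value should not simply replace the IDE value. It does not justify a one-sided rule, because a PAS rate well above the IDE rate mixes populations too.

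It is also fair that the update has no decision threshold and supports no success criterion, that a failed Objective 4 would itself be a result, and that 0.927550 is already an IDE figure. The synopsis, 3.2 and 5.1 can be read as short forms of the detailed rule in 3.1 and 7.6. Even so, none of the five places says what is reported after a failure.

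**Conclusion.** The point holds as a defect in a supplementary analysis. Five places describe the update, two with the condition and three without, and the outcome after a failed Objective 4 is left open. The condition is one-sided. Under the rule that reproduces the stated power, it keeps the superiority probability from falling below about 0.91 and withholds values such as 0.903, 0.861 and 0.779. At a true PAS rate of 0.60, the expected figure is 0.929 with the condition and 0.850 without it.

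This rests on four assumptions: the inferred fusion count of 60/104; unadjusted PAS counts with no propensity-score adjustment or imputation; 150 PAS coflex patients; and the IDE value standing when Objective 4 fails, which the plan implies but does not state. Across the readings of margin, rule and sample size tried, the floor lies between 0.865 and 0.9275. It cannot be fixed more closely until the 0.10 margin in 7.6 and the 0.1175 margin in the synopsis and 7.7.4 are reconciled.

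**What to change.** In sections 3.1 and 7.6, remove the condition on reporting. State that the updated non-inferiority and superiority probabilities relative to fusion will be shown side by side with the IDE-only values (0.999362 and 0.927550) whatever the Objective 4 result. Add a note that the PAS has no concurrent fusion arm, so the updated values combine PAS coflex patients with IDE fusion patients. Put the same rule in the synopsis, 3.2 and 5.1. Reconcile the Objective 4 margin separately; with this change the fusion figures no longer depend on it.

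The cost is wording only, with no new data. The updated figure may be less favourable than the published one.
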